Safety Monitoring Committee

Date most recently revised 3/22/2022

Protocol Version 2.5

We will appoint a Safety Monitoring Committee (SMC) for trial monitoring. This will be composed of three independent experts with relevant experience. They will receive reports and convene meetings for this study on a twice-yearly basis. They will also receive reports per occurrence of SAEs as described in the table above.

E. Potential Benefits

Phase 3: For all participants in Phases 2 and 3, we will conduct research assessments 1-month and 6-months post-hospitalization. If we identify risk for suicide at those assessments, we will work with participants to ensure that they receive appropriate treatment. Benefits to the participants receiving the LifePlans intervention may include education about and increased motivation for use of coping skills in the following areas: identification of life values and implementing values-consistent behavior; problem-solving strategies; communication with family, friends, and treatment providers; treatment adherence and engagement; and safety planning and means restriction.

All phases/ knowledge to be gained: This study will allow us to develop and pilot test a video-based self-help intervention for use at the high-risk time period of transition from psychiatric hospitalization to community outpatient treatment. We will assess acceptability, feasibility, and safety of this intervention. The proposed project, including the open trial and pilot RCT, will prepare us to conduct the next study in this line of research, i.e., a full-scale effectiveness study. Ultimately, we hope this will result in another tool to be used for suicide prevention in a high-risk clinical group.

F. Risk-Benefit Ratio

Phase 3: The risks to participants are judged to be acceptable relative to the anticipated benefits. Serious risks related to study participation are unlikely to occur. Benefits may include education if receiving the LifePlans intervention, and risk assessments and assistance obtaining appropriate treatment if needed at follow-up assessments.

4) REFERENCES

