BUTLER HOSPITAL
INSTITUTIONAL REVIEW BOARD
PROTOCOL

1.) Project

Title of Project: Development of an Adjunctive Video-Based Suicide Prevention Intervention Immediately Following Psychiatric Hospitalization

Principal Investigator (PI): [name].

Other Investigator(s): [name]., [name]., [name]., [name].

2.) Description of Study

A. Specific Aims

- 1) **Phase 3:** We will conduct a pilot RCT (n=40) of hospitalized patients (including people enrolled in a partial hospital program) with a recent suicide attempt/plan who will receive treatment as usual (TAU) plus *LifePlans* vs TAU only. We will examine *LifePlans* feasibility and acceptability (video viewing, engagement, satisfaction, recruitment/retention), treatment differences (within relevant confidence intervals) on outcomes (e.g., suicide behaviors), and change on potential mechanisms.

B. Background

Suicide and attempted suicide are major public health issues in the U.S., accounting for almost 45,000 deaths in 2016, and over 1 million attempts each year. Although recent years have seen significant advances in our knowledge of efficacious treatments for many psychiatric disorders, the suicide rates in the U.S. have been increasing since 2000. Even with increased efforts in recent years, there still has been a relative paucity of research devoted to developing or testing innovative interventions directly targeting suicidal behavior to reach those most in need. Some treatments (e.g., cognitive behavior therapies) have been found to reduce rates of suicide attempts, but these interventions require substantial training and are lengthy and costly to administer. On the other hand, minimally intensive interventions (e.g., follow-up letters, postcards) have shown mixed results. More efficient and effective “middle ground” interventions developed to prevent suicidal behavior are clearly needed. We urgently need interventions based on evidence-based principles that decrease suicidal behavior and are feasible to deliver to large numbers of patients at times when their risk for suicide is high.

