We will ask participants to complete additional assessments reflecting the content of LifePlans. Participants will complete video completion surveys of the time that they spend watching the video and the particular sections watched. If they did not watch the videos, participants will answer questions on any barriers that prevented them from watching. To assess transportation/engagement, we use a modified version of the Transportation Scale⁹ (11 items) we previously developed that is appropriate for watching a video. Sample items include: "The [video about XX] affected me emotionally" or "I found my mind wandering while [watching the video about XX]." Items are rated from 1 "not at all" to 7 "very much." The total scale score is calculated by taking the average of all items. In addition, participants will complete a Video Acceptability Scale, which is adapted from a 7-item Likert-scale measure (1=not at all and 7=very much) designed for technology-assisted interventions by Ondersma et al.¹⁰ that assesses how participants feel about their experience: overall liking, interesting, ease of use, understandable, respectful, or annoying. To assess message understanding, we will use a Message Scale, which consists of questions designed to: 1) enhance the impact of the intervention; and 2) provide data to us about their reactions to the video. The questionnaire includes these questions: 1) What did you like about this video? What did you not like about this video?; 2) What was the main message that you got from watching this video?; 3) Does this video have any relevance to your life? What relevance does it have to your life?; and 4) What might you do differently as a result of watching this video? We will use qualitative data analysis techniques to analyze participants' responses.

Research Assessments – Open Trial and Pilot RCT (phases 2 and 3)		
	Purpose	Timepoints
Treatment Acceptability, Feasibility, Uptake, Transportation		
Credibility Expectancy Questionnaire	P	BL
Client Satisfaction Questionnaire	P,O	M1
Qualitative Interview	P	M1
Video Completion Surveys	P	W1, W2, W3, W4
Transportation Scale	P	M1*
Video Acceptability Scale	P	M1*
Message Scale	P	M1*
Psychiatric Symptoms and Functioning		
Columbia Suicide Severity Rating Scale	O**	BL, M1, M6
Modified Scale for Suicide Ideation-	O	BL, M1, M6
PROMIS-29	O	BL, M1, M6
PROMIS Depression Short Form***	O	W1, W2, W3, W4
Hospital chart review	I,O	BL, M6
Psychosis Screening Questionnaire	I	BL

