Mental Help Seeking Attitudes Scale	O	BL, M1, M6
Personal Suicide Stigma Questionnaire (self-blame subscale only)	O	BL, M1, M6
Potential Mechanisms (CLASP Targets)		
Multidimensional Scale of Perceived Social Support	Med	BL, M1, M6
Brief COPE	Med	BL, M1, M6
Valuing Questionnaire	Med	BL, M1, M6
Treatment Utilization		
Treatment History Interview		BL, M1, M6
Outpatient and Hospital Chart Review		BL, M1, M6
Note. Purpose: P=Pilot study target outcome; O=Outcome in large-scale RCT; I=Inclusion criteria; O**=Primary outcome in large-scale RCT; C=Characterize sample; Med=Potential mediator in a larger scale RCT. Timepoints: BL=baseline; W1, W2, W3, W4=Week 1, 2, 3, and 4 of the intervention. M1 and M6=Month 1 and 6. M1*=M1 during the pilot RCT, but weekly during the open trial.*** The PROMIS Depression Short Form was added for the pilot RCT.		

Suicidal Behaviors. The Columbia Suicide Severity Rating Scale (C-SSRS)¹¹ will be used to assess suicide ideation, intent, plans, and behavior. C-SSRS interviews will be conducted by trained research staff supervised by [name] with consultation from Drs. [name] and [name]. Training procedures consist of: a) review of written materials, b) didactic instruction; c) practice interviews with review and feedback from senior staff; and 4) continued practice, training and feedback until high agreement with established consensus ratings are met

(e.g. 3 consecutive C-SSRS ratings are within 2 points of our consensus ratings). We will assess interviewers' reliability in an ongoing manner. Following initial training, interviewers and senior staff meet on a monthly basis to review tapes, address questions/issues, and monitor interrater reliability.

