This pilot study has the primary aims of refining interventions and research procedures for a subsequent RCT to test the efficacy of LifePlans. In the past, researchers have used pilot data to estimate an effect size to assist in future power calculations. Kraemer et al.^{26,27} emphasized the limitations of this practice due to the likelihood of large standard errors surrounding effect size estimates, and the concern that RCTs should be powered to detect a difference between groups that is considered to be a minimally clinically significant difference. In light of these concerns, we propose the following analysis plan.

Target treatment development outcomes

We will use descriptive statistics to summarize all variables. At the end of the open trial, and midway and at the end of the pilot RCT, we will examine acceptability and satisfaction outcomes for LifePlans and for the overall study. When the outcome is not met, the research team will investigate and discuss the issue, and depending on the perceived reasons for the discrepancy, may modify relevant research procedures to address the issue. For example, if uptake is low, we will try to modify instructions to participants in order to increase uptake.

D. Material Inducements

Phase 3: Similar to Phase 2, for the pilot RCT (n = 40), we will pay participants for assessment interviews: \$20 for baseline, and \$40 for Month 1 and 6 assessments (up to \$100). We will also pay participants \$5 for each weekly survey they complete (up to \$20 total). Therefore, they may receive up to \$120 total for their participation. We will also provide transportation if needed for appointments.

E. Training of Research Personnel

All study staff will have undergone mandatory online education in human research participants' protection. PIs and research assistants will have training in Good Clinical Practice via an online program. All study staff will undergo specific training relevant to their study roles and responsibilities. Training will be documented via collection of training certificates.

3) Human Subjects

A. Subject Population

Phase 3: Participants (n=40) will be randomized to receive TAU vs TAU + LifePlans starting during their hospitalization and continuing after discharge.

Participants must meet the following criteria (same as Phase 2):

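### Does the Transportation Scale score go wrong because reverse-scoring is not written down?

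*Combined protocol and SAP*

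**What the plan says.** Section C2 (Study Design, Research Assessments) introduces the instrument: "we use a modified version of the Transportation Scale⁹ (11 items) we previously developed that is appropriate for watching a video". The construct is named in the same sentence as transportation or engagement. Two sample items are given, both under one set of anchors from 1 (lowest agreement) to 7 (highest):

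- "The [video about XX] affected me emotionally"
- "I found my mind wandering while [watching the video about XX" (the sample item ends there, apart from its closing bracket)

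The scoring rule is one sentence: "The total scale score is calculated by taking the average of all items". Neither the direction of the score nor any recoding is mentioned.

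The assessment table marks the scale P, which its note defines as "P=Pilot study target outcome", and schedules it at Month 1 in the pilot RCT. Section 2A (Specific Aims) lists engagement among the feasibility and acceptability targets: "feasibility and acceptability (video viewing, engagement, satisfaction, recruitment/retention". Section C4 (Data Analysis) adds only this for scores of this kind: "We will use descriptive statistics to summarize all variables".

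**The concern.** The two sample items run in opposite directions. A 7 on the emotional-effect item means the viewer was absorbed; a 7 on the mind-wandering item means the viewer was not. A programmer who took the scoring sentence literally would average both as answered. With the other ten answers held fixed, more mind wandering would then raise the engagement score.

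This matters more than usual because the analysis is descriptive. The level of the score is itself the result, so a shifted level would misstate how engaging the videos were. The scale is a pilot target outcome and engagement is named in the aim. Section C4 also has the team look at acceptability and satisfaction midway through and at the end of the pilot RCT, and possibly adjust procedures when an outcome is not met. The scale was given weekly in the open trial and at Month 1 in the RCT, so an unwritten key could in principle be applied differently in the two phases.

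**Working it through.** The plan gives no expected value, threshold or power figure for this scale, so there is nothing of its own to reproduce. The check is how far a literal reading could move the score.

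**Inputs (section C2).** There are 11 items, each answered 1 to 7, so the midpoint is 4 and a reversed answer is 8 minus the raw answer. The text shows at least one negatively worded item. The total number, k, is not given.

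**Error for one participant, k = 1.** Let n be the raw mind-wandering answer. The other ten answers cancel:

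literal total − reversed total = [n − (8 − n)]/11 = (2n − 8)/11

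| n | 1 | 2 | 3 | 4 | 5 | 6 | 7 |
|---|---|---|---|---|---|---|---|
| error | −0.55 | −0.36 | −0.18 | 0 | +0.18 | +0.36 | +0.55 |

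**Shift in the group mean, k = 1.** The same formula applies to the item mean. If mind wandering averaged 2, the shift would be (4 − 8)/11 = −0.36; if it averaged 3, (6 − 8)/11 = −0.18. Both item means are assumed for illustration.

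**A consistent viewer, k = 1.** Someone at engagement level x answers x on ten items and 8 − x on the negative one:

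literal total = [10x + (8 − x)]/11 = (9x + 8)/11

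| x | 1 | 2 | 5 | 6 | 7 |
|---|---|---|---|---|---|
| literal total | 1.55 | 2.36 | 4.82 | 5.64 | 6.45 |

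The slope is 9/11 = 0.818, so distances from 4 shrink by 18.2%. The slope is positive, so a more engaged consistent viewer still scores higher than a less engaged one.

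**The pull toward 4 is not universal.** With 5 on all ten positive items and 6 on mind wandering, the literal total is (50 + 6)/11 = 5.09 and the reversed total is (50 + 2)/11 = 4.73. Here the literal score lies farther from 4.

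**More negative items (k assumed).** The slope is (11 − 2k)/11.

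| k | 1 | 2 | 3 | 4 |
|---|---|---|---|---|
| slope | 0.818 | 0.636 | 0.455 | 0.273 |
| literal total for a viewer at 7 | 6.45 | 5.91 | 5.36 | 4.82 |

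The ordering would invert only at k = 6 or more, where the slope is (11 − 12)/11 = −0.091 or lower.

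**What uses the score.** Section C4 gives no numeric target for transportation and no test of it. Its mid-trial and final reviews name acceptability and satisfaction, with uptake as the worked example, and lead to discussion by the team. The trial size of 40 does not rest on this scale. Six other measures also carry the P mark: the credibility and satisfaction questionnaires, the qualitative interview, the video completion surveys, the Video Acceptability Scale and the Message Scale.

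**The case for a change.** The strongest case for a change is that this is the one scale here for which the protocol writes out a total, and the written rule leaves out a step that its own example shows to be needed. The team modified the scale, so the citation does not by itself supply a key for these 11 items. An outside analyst working only from this document could compute the wrong score, and one clause would prevent that.

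The text is indeed silent, and the arithmetic above holds if the step is skipped. The inference that the step will be skipped does not stand. The sentence says that the total is a mean and not a sum, which is equally true of a mean of items turned to point the same way. The people scoring the scale are those who developed this version and chose the mind-wandering item as an example. The protocol does not set out item keying for its other instruments either: the Video Acceptability Scale mixes liking with annoyance and gives no key. Leaving the key to the scoring instructions is in line with the level of detail throughout.

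The possibility of several negative items makes the worst case larger, but it also makes an unkeyed score less plausible, because the need to reverse would be harder to overlook.

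**Conclusion.** No change is needed. This is a routine scoring step left unwritten, which analysts can be expected to fill sensibly; the plan does not prescribe a wrong score.

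If the one negative item shown were averaged unreversed, a total would be off by at most 0.55 points on the 1 to 7 scale, and consistent viewers would lose about 18% of their distance from the midpoint while keeping their order. Larger effects need a count of negative items that the document does not give. Whether any error exists depends on the team's scoring key, which is also not in the document.

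Even in the unfavourable case the damage is limited and reversible. The item answers are collected either way, so the total can be recomputed, and no stated threshold, between-arm test or sample size depends on it. If the protocol is revised for other reasons, a clause saying that negatively worded items are recoded as 8 minus the answer, and that higher means more transported, would be a harmless courtesy to the reader.

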Assessments will be conducted: 1) to assess feasibility and acceptability, uptake, transportation, and understanding of key messages; 2) to assess inclusion criteria; or 3) to pilot outcome measures or potential mediators for the eventual large-scale RCT. See the table below for the purpose of each instrument and the assessment schedule. A trained research assistant will conduct all assessments. After the baseline assessment, we will conduct assessments at 1- and 6-months post-discharge. We will also administer weekly post-video surveys in order to assess completion and acceptability ratings.

Treatment acceptability/feasibility. Intervention credibility and patient expectations for intervention success after viewing the first episode will be measured with the Credibility Expectancy Questionnaire (CEQ).⁶ The Client Satisfaction Questionnaire (CSQ-8)^{7,8} will be used post-treatment to assess satisfaction with interventions. We will also use qualitative responses to a detailed post-treatment interview to gain participants'

feedback about interventions and research procedures, including whether there was any contamination between arms, with participants in LifePlans sharing videos or video content with participants in the treatment as usual arm.

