We will use several strategies to increase retention for assessments. Research staff will remind participants about appointments, maintain a list of locator contacts for each participant, reach out to contacts as needed, schedule assessments regardless of intervention participation, and have flexibility in when assessments are scheduled. Finally, we will provide transportation if needed for appointments.

Phase 3: Pilot RCT

The aim is to conduct a pilot RCT (n=40), with participants randomized to treatment as usual (TAU) or TAU + LifePlans. We will enroll hospitalized patients with a suicide plan/attempt prior to admission in the past month (see full inclusion criteria below). Methods will be similar to those described in the open trial (see previous section for Phase 2), with only the differences noted below. We will continue to focus on acceptability and feasibility, including an evaluation of the proposed research design.

Phase 3: Control condition description and rationale

The control condition will be TAU, which, as noted above, will include Hospital Safety and Discharge Planning as part of inpatient care, followed by outpatient care at a CNE outpatient site. In choosing TAU as a control condition, we considered the nature of the LifePlans intervention. LifePlans is designed to be adjunctive to TAU and in fact to encourage adherence to outpatient treatment plans developed in the hospital. We did not choose a more robust control condition because LifePlans is designed to be a lower-intensity intervention (thus increasing its potential reach) and not to replace existing treatments (but, in fact, to enhance them).

Phase 3: Randomization

Participants will be randomized using a 1:1 ratio to either TAU or TAU + LifePlans. Randomization will be stratified by: a) gender (male/ female/ non-binary) and b) suicide attempt vs. plan prior to admission. Treatment arm assignments will be blocked in blocks of 4 or 6 participants (randomly ordered). A staff member with no other study responsibilities will set up randomization tables in REDCap, and other research staff will not have access to the tables. Participants will be randomized following the baseline assessment using the randomize feature in REDCap. This ensures allocation concealment.

C3. Specific Procedures or Treatments

See C2. Study Design.

C4. Data Analysis

Date most recently revised 3/22/2022

Protocol Version 2.5

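### Does the pilot's rule for acting when an outcome is not met need a fixed target, an uptake denominator and a defined midway point?

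*Combined protocol and SAP*

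**What the plan says.** C4, under Target treatment development outcomes, provides that at the end of the open trial and also "midway and at the end of the pilot RCT, we will examine acceptability and satisfaction outcomes for LifePlans and for the overall study". It continues: "When the outcome is not met, the research team will investigate and discuss the issue". Depending on the perceived reasons, the team may then modify procedures. The example given is that "if uptake is low, we will try to modify instructions to participants in order to increase uptake". The same section summarises all variables descriptively and makes refinement of the intervention and research procedures the primary aim.

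The data behind uptake are described in C2, Research Assessments: "Participants will complete video completion surveys of the time that they spend watching the video and the particular sections watched". Participants who did not watch are asked about barriers. The assessment table schedules these surveys at weeks 1 to 4.

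Three statements bear on the first episode. In C2, credibility and patient "expectations for intervention success after viewing the first episode will be measured with the Credibility Expectancy Questionnaire". The assessment table, which covers both the open trial and the pilot RCT, lists the "Credibility Expectancy Questionnaire" at baseline. Under Phase 3: Randomization, "Participants will be randomized following the baseline assessment".

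Phase 3: Pilot RCT says the methods follow the open trial except where noted, and sends the reader to a Phase 2 section that is not in the text available.

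**The concern.** A rule that acts when an outcome is not met presupposes a criterion, and none can be found. The table's code P marks instruments as pilot target outcomes but gives no value. Nothing says how much viewing counts as uptake, or whether people who return no survey stay in the denominator. Midway could mean 20 randomised, 20 past Month 1 or half the calendar time. Because refinement is the stated aim, two readers of the same data might disagree on whether to change something midway, and on what to carry into the larger RCT.

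The first episode adds a second worry. Taken literally, a questionnaire given after episode 1, listed at baseline, in a trial that randomises after baseline, would have everyone viewing an episode before allocation. The plan itself asks at Month 1 about sharing of videos, "including whether there was any contamination between arms", so exposure of the TAU arm would matter. There are also five episodes against four weekly surveys.

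**Working it through.** **Inputs from the protocol.** n = 40, randomised 1:1, so 40/2 = 20 expected in LifePlans. Five episodes. Weekly surveys are paid at $5 each up to $20, so 20/5 = 4 surveys, which matches the table. The plan gives no target, power or precision figure, so there is no plan figure to reproduce. Every target, viewing rate and return rate below is an assumption.

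**1. Can the denominator flip the verdict?** Yes. Take a 70% target and 20 in LifePlans, of whom 16 return surveys and 12 view enough.
- Responders: 12/16 = 75%, met.
- All randomised: 12/20 = 60%, not met.

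How often this happens depends on the inputs. Let R ~ Bin(20, return rate) and V ~ Bin(R, viewing rate among responders). The verdicts differ when V ≥ 0.7R and V < 14. With a 75% viewing rate, that has probability 0.59, 0.44 and 0.20 at 70%, 80% and 90% survey return. With a 50% viewing rate it is 0.07, 0.05 and 0.03. The ambiguity is real, but its size comes from the assumptions.

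**2. Would a fixed target settle the matter?** Let X ~ Bin(n, p) be the number with adequate uptake.

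| n | Target | True uptake | P(met) | P(not met) |
|---|---|---|---|---|
| 20 | 60% (X ≥ 12) | 70% | 0.89 | 0.11 |
| 20 | 70% (X ≥ 14) | 70% | 0.61 | 0.39 |
| 20 | 80% (X ≥ 16) | 70% | 0.24 | 0.76 |
| 10 | 70% (X ≥ 7) | 70% | 0.65 | 0.35 |
| 10 | 70% (X ≥ 7) | 80% | 0.88 | 0.12 |
| 10 | 70% (X ≥ 7) | 50% | 0.17 | 0.83 |

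The exact 95% interval is 46% to 88% for 14/20 and 35% to 93% for 7/10. If midway means 20 randomised, simulation of the stratified blocks puts 8 to 12 in LifePlans (central 95%). At these sizes, a crossing of any chosen line is weak evidence.

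**3. Would counting a missing survey as not viewed help?** It makes the rule definite, but it mixes two problems. Suppose 80% truly view enough and survey return is independent of viewing.
- Full return: P(X ≥ 14) = 0.91.
- 90% return: recorded uptake 0.80 × 0.90 = 0.72, so P(X ≥ 14) = 0.68.
- 80% return: recorded uptake 0.80 × 0.80 = 0.64, so P(X ≥ 14) = 0.38.

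A strict rule of this kind would often report low uptake when the trouble was survey return. A team looking at viewing, barriers and non-return separately would not make that mistake.

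**4. The first episode.** The Specific Aims, C1 and Phase 3: Pilot RCT all define the comparison as TAU against TAU plus LifePlans, so viewing by the TAU arm is excluded by design. The assessment table serves both phases, and in an open trial a baseline label raises no allocation problem. The likely reading is that LifePlans participants complete the questionnaire soon after randomisation, at the start of the intervention.

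**5. Five episodes and four surveys.** Nothing says that one survey covers one episode; the surveys record time and sections watched. The intervention starts during the hospital stay, so an episode there followed by four weekly ones would fit. No conflict is shown.

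**The case for a change.** The strongest case for a change is that this rule is the stated mechanism for the pilot's primary aim. Without a criterion it cannot be applied uniformly or audited afterwards. A short table and a few sentences would cure that, and a missing Phase 2 section cannot explain the mismatch over the credibility questionnaire, since all three statements are in the text.

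Part of this stands. The text does not let an outside reader decide whether an outcome was met, and the questionnaire's timepoint does not agree with its description. What does not follow is that the trial would be run or read differently. C4's own wording, with its definite article and its heading on target outcomes, reads as if it points back to targets already listed, and the cited Phase 2 section is a natural place for them. If they are there, the gap is a missing cross-reference. If they are not, the team still has viewing time, barriers, ratings and counts, and discretion over what to do with them. Any particular threshold, such as a number of episodes or minutes, would be the reviewer's preference rather than something the documents support.

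**Conclusion.** No change to the plan is needed. The missing target, denominator and midway date are gaps in a discretionary refinement rule that analysts can fill sensibly: report viewing among all randomised to LifePlans and among responders, show survey non-return separately, and date any procedural change. Descriptive reporting of all variables already allows this. The baseline label on the credibility questionnaire is most likely a clerical looseness, because the arm definitions rule out TAU viewing.

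In size, the ambiguity can turn 60% into 75% on one assumed set of counts, but it alters no between-arm estimate, error rate or power. A fixed cut-off at 10 to 20 participants would misclassify often enough that informed discussion is a fair alternative.

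This rests on the rule staying advisory, as C4 words it, and on the baseline label not being meant literally. If a target were to decide automatically whether the larger RCT proceeds, or if TAU participants were in fact shown an episode, the point would need to be reopened.
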